5.6 MEASURES

Table 4. Summary of measures.

Timing	Measure	How it will be measured
First Online Questionnaire – After reading hypothetical high air pollution scenario	Baseline intentions ^a to adopt protective behaviours in response to hypothetical, high air pollution alert	Assuming the situation described was happening right now, how much would you agree with the following statements? 
 - I intend to follow the recommendations received with the air alert to reduce exposure to air pollution - I will avoid going outdoors - I intend to reduce length or level of my physical activity outdoors - I intend to change my travel route - I intend to change my exercise location - I intend to change the time when I travel - I intend to change the time when I exercise outdoors
	Baseline medication adherence intentions ^a	If you have lung problems: 
 - I intend to use my preventer inhaler daily - I intend to carry my reliever inhaler with me
	Other baseline intention ^a (not advised behaviours)	
 - I will wear a mask as a protection from air pollution - I intend to reduce length or level of my physical exercise indoors
	Previous protective behaviour ^b	- In the past 4 weeks, how often have you taken action to reduce exposure to air pollution, I response to hearing or reading an air quality forecast?
	Planning	
 - In the last 4 weeks, to reduce your exposure to air pollution, have you considered making permanent changes to your daily travel route or exercise place and time?^c - In the last 4 weeks, how often have you checked air quality information before doing physical activity outdoors?^b
	Physical activity ^d	- To stay healthy, the NHS recommends at least 150 minutes of moderate physical activity (e.g. cycling, fast walking, swimming) every week (e.g. 30 minutes 5 days a week). Based on this, how physically active were you in the last week?
	Symptoms ^c	- Have you ever experienced symptoms caused by air pollution?
Air Alert period – Online questionnaires	Alert recall ^e	- Recently we sent you an air quality alert about poor air quality. What was the level of air pollution reported?
	Actual Behaviour change ^c	In response to receiving the air quality alert: 
 - I reduced length or level of my physical activity outdoors - I changed my travel route - I changed my exercise location - I changed the time when I travelled - I changed the time when I exercised outdoors - If you answered no, please report the reasons [text box].
	Medication adherence ^c	If you have lung problems: 
 - I used my preventer inhaler daily - I carried my reliever inhaler with me when going outdoors. - If you answered no, please report the reasons [text box].
Final Online Questionnaire – at 4 weeks	Behaviour change at 4 weeks ^b	- In the past 4 weeks, how often have you taken action to reduce exposure to air pollution, I response to hearing or reading an air quality forecast?
	Physical activity ^d	- To stay healthy, the NHS recommends at least 150 minutes of moderate physical activity (e.g. cycling, fast walking, swimming) every week (e.g. 30 minutes 5 days a week). Based on this, how physically active were you in the last week? ^e
	Action planning	
 - In the last 4 weeks, to reduce your exposure to air pollution, have you considered making permanent changes to your daily travel route or exercise place and time?^c - In the last 4 weeks, how often have you checked air quality information before doing physical activity outdoors?^b
	Worry ^a	Adapted from Witte et al. (34) 
 - The information received through the CityAir app made me worry about the possibility of suffering health effects from exposure to air pollution

	- The information received through the CityAir app made me nervous and tense about the possibility of suffering health effects from exposure to air pollution
Severity ^a	Adapted from Witte et al. (34)
	- Air pollution is a severe threat to my health
Conditional susceptibility ^f	- How likely do you think you are to suffer from health effects due to air pollution if you do not take any action to reduce exposure? - How likely do you think people of your same age and sex are to suffer from health effects due to air pollution if they do not take any action to reduce exposure?
Response efficacy ^a	Adapted from Witte et al. (34)
	- Following the health advice received through the CityAir app is effective in protecting me from exposure to air pollution
Medication response efficacy ^a	If you have lung problems: - Taking my preventer medications daily is effective in helping me to control my asthma - Carrying my reliever medication with me is an effective way to protect my health
Self-efficacy ^a	Items adapted from Witte et al (34) and Rhode et al (35)
	- I am confident I would be able to follow the health advice received through the CityAir app, if I wanted to
Medication self-efficacy ^a	Items adapted from Witte et al (34) and Rhode et al (35)
	- If you have lung problems: I am confident I would be able to take my preventer inhaler every day , if I wanted to - I am confident I would be able to remember to carry my reliever inhaler with me during days of poor air quality, if I wanted to
Response costs ^a	- I do not have enough time to follow the health advice received through the CityAir app - Taking side roads makes my journey too long
Medication response costs ^a	If you have lung problems: - Using the preventer inhaler daily is not safe - Using the preventer inhaler daily makes me dependent on it
Unwanted consequences of intervention ^a	- In the last 4 weeks I stopped exercising altogether due to receiving alerts about poor air quality - In the last 4 weeks, I made an emergency /unplanned visit to A&E or visited my GP due to symptoms caused by air pollution
Sensory cue prevalence ^a	- I trust my own perception of air quality more than any official air quality alert
Credibility ^g	- Meyer's credibility index (36,37) (α=.67)
Clarity ^h	- Overall, how clear were the messages received?
Perceived informed choice ^a	- I received enough information to make an informed choice on how to reduce my exposure to air pollution
Intentions ^a to adopt protective behaviour in response to hypothetical, high air pollution alert	[After reading again the high air pollution hypothetical scenario and tailored advice] - I intend to follow the recommendations received with the air alert to reduce exposure to air pollution - I will avoid going outdoors - I intend to reduce length or level of my physical activity outdoors - I intend to change my travel route - I intend to change my exercise location - I intend to change the time when I travel - I intend to change the time when I exercise outdoors
Medication adherence intentions ^a	If you have lung problems: - I intend to use my preventer inhaler daily - I intend to carry my reliever inhaler with me
Other intentions (not advised behaviours) ^a	- I will wear a mask as a protection from air pollution - I intend to reduce length or level of my physical exercise indoors

Notes: ^a Measured on 9-point scales, where 1=strongly disagree to 9=strongly agree; ^b From 1 Not at all to 9 all of the time; ^c Possible answers: yes, no, not sure; ^d From 1 Not at all, to 7 more than 150 minutes; ^e Possible answers: Low, Moderate, High, Very High, Not sure, I did not receive any alert; ^f From 1=not at all likely to 9=extremely likely; ^g on a 5-point scale; ^h 1= not clear at all to 9= extremely clear. Demographic data will be collected for all the participants in the first questionnaire.

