5.3 SAMPLE

Inclusion criteria

Inclusion:

- Users of air alert systems managed by the ERG
- Age: > 18 years
- Working or living in Greater London.

Exclusion criteria

- younger than 18 years
- not working or living in Greater London
- no longer users of the air quality alert smartphone application.

Sampling

Sample size was calculated using the G*Power statistical power analysis (32), to give 80% power to detect a statistically significant difference in the main outcome measures at $\alpha=0.05$, if a small to medium effect size of $f=0.02$ or higher is observed (9), adjusting for one covariate. Given the possibility of dropout, we inflated the sample size by 20%, and aimed to achieve a minimum sample size of $n=240$.

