Moderate 4-6	Enjoy your activities as usual ^a	Adults and children with lung problems, and adults with heart problems, who experience symptoms, should consider reducing strenuous physical activity, particularly outdoors. ^b	
Enjoy your activities as usual. However, if you wanted you, you can reduce your exposure to pollution by reducing levels and length of physical activity outdoors.
 
You can also consider changing:
 
 • Travel route or • Exercise location (e.g. use our app to find less polluted roads or parks) or • Time (e.g. mornings or less polluted times). ^e 	
Adults and children with lung problems, adults with heart problems, and older people, should reduce levels and length of physical activity outdoors.
 
Where possible, change:
 
 • Travel route or • Exercise location (e.g. use our app to find less polluted roads or parks) or • Time (e.g. mornings or less polluted times). ^h
High 7-9	Anyone experiencing discomfort such as sore eyes, cough or sore throat should consider reducing activity, particularly outdoors. ^c	Adults and children with lung problems, and adults with heart problems, should reduce strenuous physical exertion, particularly outdoors, and particularly if they experience symptoms. People with asthma may find they need to use their reliever inhaler more often. Older people should also reduce physical exertion. ^d	
Anyone who experiences sore eyes, cough or sore throat should consider limiting their exposure to air pollutants.
 
To do this, you don't need to stay indoors, instead you can reduce levels and length of physical activity outdoors.
 
You can also consider changing:
 
 • Travel route or • Exercise location (e.g. use our app to find less polluted roads or parks) or 	
Adults and children with lung problems, adults with heart problems, and older people, should reduce levels and length of physical activity outdoors.
 
People with asthma may find they need to use their reliever inhaler more often.
 
Where possible, change:
 
 • Travel route or • Exercise location (e.g. use our app to find less polluted roads or parks) or

SHORT TITLE/ACRONYM: Improving the health impact of air quality alerts v.3

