			
 • Time (e.g. mornings or less polluted times).ⁱ 	
 • Time (e.g. mornings or less polluted times).ⁱ
Very high 10	Reduce physical exertion, particularly outdoors, especially if you experience symptoms such as cough or sore throat. ^e	Adults and children with lung problems, adults with heart problems, and older people, should avoid strenuous physical activity. People with asthma may find they need to use their reliever inhaler more often. ^f	
Reduce levels and length of physical exertion, in particular outdoors, even more so if you experience symptoms such as cough or sore throat.
 
Where possible, change:
 
 • Travel route or • Exercise location (e.g. use our app to find less polluted roads or parks) 
or
 
 • Time (e.g. mornings or less polluted times).^l 	
Adults and children with lung problems, adults with heart problems, and older people, should avoid intense physical activity.
 
People with asthma may find they need to use their reliever inhaler more often.
 
Where possible, change:
 
 • Travel route or • Exercise location (e.g. use our app to find less polluted roads or parks) 
or
 
 • Time (e.g. mornings or less polluted times).ⁱ

Note: For each message word count and readability score are reported (i.e. higher scores indicate more complex sentences). a. Word count: 5, readability score: 12 (It should be easily understood by 17 to 18 year olds); b. Word count: 22, readability score: 20; c. Word count: 17, readability score: 18 (understood by 23 to 24 year olds); d. Word count: 45, readability score: 14 (understood by 19 to 20 year olds); e. Word count: 16, readability score: 16 (understood by 21 to 22 year olds); f. Word count: 32, readability score: 12; g. Word count: 53, readability score: 7 (understood by 12 to 13 years old); h. Word count: 49, readability score: 8 (understood by 13 to 14 years old); i. Word count: 62, readability score: 8; l. Word count: 50, readability score: 8. These messages were reviewed by both the ERG and PPI groups.

SHORT TITLE/ACRONYM: Improving the health impact of air quality alerts v.3

Table 3 A few examples of additional messages developed and aiming to target specific psychosocial factors.

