	Before you go out walking, jogging or cycling check our App to find less polluted areas where exercising. Start by exploring green areas and parks close to your house or office.	Before you go out walking, jogging or cycling check our App to find less polluted areas where exercising. Start by exploring green areas and parks close to your house or office.	Before you go out walking, jogging or cycling check our App to find less polluted areas where exercising. Start by exploring green areas and parks close to your house or office.	Before you go out walking, jogging or cycling check our App to find less polluted areas where exercising. Start by exploring green areas and parks close to your house or office.	Before you go out walking, jogging or cycling check our App to find less polluted areas where exercising. Start by exploring green areas and parks close to your house or office.
			People with asthma may worry about using their preventer inhalers every day. However, you should know that these medications are safe to use daily. They should also reduce your need for the reliever inhaler		People with asthma may worry about using their preventer inhalers every day. However, you should know that these medications are safe to use daily. They should also reduce your need for the reliever inhaler

SHORT TITLE/ACRONYM: Improving the health impact of air quality alerts v.3

The table reports the specific variable targeted by the messages, and who is the target of the messages. Although the majority of messages targeting the at-risk group are identical, some are slightly adjusted depending on whether people had a pre-existing lung and/or heart disease, or if they report to be at risk for other conditions including old age. This is to make sure that participants are not receiving messages irrelevant to them, as this may lead to confusion, loss of interest, and mistrust (e.g. (33)). The average readability scores were 9.3 (i.e. easily understood by 14 to 15 year olds) and 9.8 (i.e. easily understood by 15 to 16 year olds), for the general population and at-risk groups (all messages considered) respectively. These messages were reviewed by both the ERG and PPI groups.

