6. STATISTICAL ANALYSES

6.1 Quantitative data

ANCOVAs will be performed for all the intentions measures in relation to the high air pollution hypothetical scenario, adjusting for baseline measures collected about one month earlier (target population and intervention/control group entered as fixed factors). Both main and interaction effects will be tested. ANCOVAs will also be performed for the actual behaviour change at 4 weeks (with the intervention/control group entered as fixed factor). These latter analyses will also be ran in the subgroups of healthy and at-risk participants. Chi square tests will be performed to analyse differences in proportion of self-reported actual behaviour change between groups, in relation to a real moderate air pollution episode. A two-way MANOVA (1000 bootstraps) will test whether there are differences between groups (both main effects and interactions) in perceived susceptibility, worry, severity, perceived response efficacy, perception of time, self-efficacy, trust, clarity, credibility and perceived informed choice measures. Multiple linear regressions will be used to assess the associations between main predictor variables and self-reported behaviour change at 4 weeks. Mediations effects of predictor variables on significant behavioural changes will be tested using PROCESS macro (38).

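### Primary question 1 has no named intention outcome, block score or multiplicity rule, and the item on avoiding going outdoors is grouped with the protective intentions although no message shown advises it

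*Combined protocol and SAP*

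**What the plan says.** Question 1 (Section 4) asks about adherence intentions in a hypothetical high-pollution scenario. It predicts that the enhanced messages will strengthen intentions to adhere to the recommendations. No item or score is named there.

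Section 6.1 states that "ANCOVAs will be performed for all the intentions measures in relation to the high air pollution hypothetical scenario". Each model adjusts for the measure taken about a month earlier, has message group and target population as fixed factors, and tests main effects and the interaction. Section 5.3 sizes the trial "to give 80% power to detect a statistically significant difference in the main outcome measures" at 0.05. The outcomes are plural and not identified.

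Table 4 (Section 5.6) sets out the intentions, all on 9-point scales, in three blocks at both questionnaires:
- seven items under intentions "to adopt protective behaviours in response to hypothetical, high air pollution alert", including "I will avoid going outdoors";
- two medication items for people with lung problems;
- two items labelled as not advised (wearing a mask, exercising less indoors).

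The messages are in Section 5.5. At the High level, the enhanced text for the general public tells readers there is no "need to stay indoors, instead you can reduce levels and length of physical activity outdoors". A Table 3 example given to all five intervention columns begins "Before you go out walking, jogging or cycling check our App to find less polluted areas where exercising". The title of Table 3 describes its content as "A few examples of additional messages developed and aiming to target specific psychosocial factors". The alert questionnaire's list of actual behaviours starts with "I reduced length or level of my physical activity outdoors" and continues with travel route, exercise location, time of travel and time of exercise. It has no item on avoiding going outdoors.

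**The concern.** There are two linked problems. First, no outcome or score is fixed in advance for a primary question, so a significant message effect on any intention block or item could be presented as the answer to it.

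Second, prediction A is about following recommendations, yet one of the items counted as protective is something no displayed message recommends. For the general public, a message that works as written could lower agreement with that item while raising the others. Any score that includes it would then understate the effect, and a single-item test of it could point the opposite way from the prediction.

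**Working it through.** **The plan's own figure.** Inputs from Section 5.3: 80% power, 0.05, one covariate, 20% inflation, n = 240. I used an ANCOVA F test with 1 numerator degree of freedom and noncentrality f²N. At the printed f = 0.02 this needs 19,625 evaluable participants. Reading f as 0.2 (an assumption) it needs 199, and 199 × 1.2 = 239, close to 240. The effect size is a separate matter. What matters here is that the sample size is consistent with one test at 0.05.

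**False positives.** I count only the message main effect, with each of k tests two-sided at 0.05. For independent tests the chance of at least one false positive is 1 − 0.95^k. For equal correlation ρ it is 1 − ∫[Φ((c − √ρ z)/√(1−ρ)) − Φ((−c − √ρ z)/√(1−ρ))]^k φ(z) dz, with c = 1.960. The documents give no correlations, so ρ is assumed.

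| Tests | ρ = 0 | ρ = 0.7 |
|---|---|---|
| 1 named outcome | 5% | 5% |
| 2 blocks (protective, medication) | 9.8% | 8.4% |
| 3 blocks (not-advised added) | 14% | 11% |
| 7 protective items | 30% | 18% |

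**The outdoors item against the messages.** I compared the item with what is displayed.
- Table 2, both arms and all levels: the advice is to reduce activity or exertion, to avoid strenuous or intense activity, or (enhanced only) to change route, location or time. None advises avoiding going outdoors.
- Table 2, enhanced High text, general public: staying indoors is said to be unnecessary.
- Table 3 examples: none advises it, and one presupposes going out.
- Alert questionnaire: the five specific behaviours are carried over and this one is not.
- Section 1.1.5 lists spending more time indoors among common responses in the literature, which is a reason to ask the item.

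**Effect on a score.** The standardised effect of a k-item mean is the mean item effect divided by √((1 + (k−1)ρ)/k). Take a mean of the five specific behaviours as the reference, at 80% power (noncentrality 1.960 + 0.842 = 2.802). Power of another score is then Φ(2.802 × ratio − 1.960). For a seven-item mean, six items are assumed to have effect d and the outdoors item varies. The ranges cover ρ = 0.3 to 0.7 among the other items.

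| Outdoors item | Correlated like the rest | Uncorrelated with the rest |
|---|---|---|
| moves with the others (+d) | 81% to 84% | 90% |
| does not move | 68% to 71% | 79% to 80% |
| reverses in half the sample (−d/2 overall) | 61% to 64% | 72% |
| reverses in everyone (−d) | 53% to 56% | 64% |

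One line in full, at ρ = 0.5, common correlation, item not moving: the ratio is (6/7)/√(4/7) ÷ 1/√(3/5) = 0.878, and Φ(2.802 × 0.878 − 1.960) = 69%.

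**The two candidate outcomes.** A single item sharing the common effect has ratio √((1 + 4ρ)/5) = 0.663, 0.775 and 0.872 at ρ = 0.3, 0.5 and 0.7, so power is 46%, 58% and 69% where the five-item mean has 80%. The five-item mean has its own weakness, because the enhanced text offers route, location or time as alternatives. If those four items move half as much as reducing activity, the mean effect is (1 + 4 × 0.5)/5 = 0.6 of the assumed one, and power is Φ(2.802 × 0.6 − 1.960) = 39%.

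**The case against.** The strongest reply is that Table 4 treats each block as one measure, so Section 6.1 may intend block scores. If the lung-only medication block is also set aside as a separate question, one protective measure remains and the error rate is 5%. That reading is reasonable, but no block score is defined and the protective block still contains the outdoors item.

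A second reply is that the block is titled protective, not advised, and that Section 1.1.5 counts avoiding outdoor activities as adherence in earlier studies. That supports asking the item. It does not make the item a recommendation of this trial, and Table 4 has a separate group for behaviours not advised. The statement that staying indoors is unnecessary appears only in the general-public High text. The scenario wording and the remaining Table 3 messages are not shown, so the point is limited to what is displayed.

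A reader might infer several stronger things that the documents do not support:
- That there is no significance level. Section 5.3 states 0.05; what is missing is which test it governs and how several tests are handled.
- That the error rate for question 1 is 30%. That needs seven independent single-item tests, and the plan does not say items are tested singly.
- That power is certainly lost. The plan does not specify a seven-item mean, and the loss nearly vanishes if the outdoors item is uncorrelated with the rest and does not move.
- That a five-behaviour mean is the only proper outcome. In Table 2, four of its behaviours are named only in the enhanced High message, whereas the global item on following the recommendations fits prediction A directly.
- That the first-questionnaire measure is contaminated. Section 5.4.2 places randomisation before it and asks about advice given, and Table 4 has the scenario re-read with tailored advice at the end. Whether the first advice was arm-specific is not settled.

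**Conclusion.** The point holds. As written, question 1 can be answered by any of several intention measures, with a false-positive chance of about 8% to 10% across the protective and medication blocks, or 18% to 30% across seven single items. These ranges rest on assumed correlations of 0.7 to 0.

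The outdoors item is inconsistently grouped on the protocol's own categories and displayed messages. Its effect on a score ranges from no loss to power of roughly 53% to 64% instead of 80%. That range depends on assumed equal effects on the other items, on the correlations, and on how far the item reverses, none of which the documents give. The change should be made: it affects how a primary result can be read, and the repair is textual.

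**What to change.** 1. Keep asking the outdoors item in both questionnaires, but analyse it with the not-advised behaviours, outside any adherence outcome.
2. In Section 6.1, before data are seen, name one primary intention outcome for question 1, measured at the final questionnaire, with the message main effect tested at 0.05. The global item on following the recommendations received with the alert matches prediction A and applies to both arms. A mean of the advised items, without the outdoors item, is an acceptable alternative if the protocol states that four of its five behaviours appear only in the enhanced High message. Treat the other intention measures as secondary, with a stated multiplicity adjustment, or report them descriptively.
3. Confirm that first-questionnaire intentions are recorded before any arm-specific advice is shown. If they are not, do not use them as the covariate for question 1, because adjusting for them could absorb part of the effect being tested.

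Cost: one item regrouped and a few sentences in Section 6.1. No question is dropped and the target of 240 stands. The 5% covers question 1 only, not all three primary questions.

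Downsides: secondary items lose power. With seven of them (five specific behaviours, two medication), 200 evaluable and f = 0.2, power of 80% at 0.05 becomes 54% at 0.05/7 = 0.00714, and less for the lung-only pair. A single global item is less precise than a multi-item mean. Dropping the covariate, if step 3 requires it, costs further precision by an amount the documents do not allow one to calculate.

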4 RESEARCH QUESTION/AIM(S)

The purpose of the present study is to test whether theory and evidence-based alternative communication formats, targeting message specificity and previously identified psychosocial predictors of adherence, could improve the behavioural impact of existing alert systems, compared to the official messages sent in association with the UK AQIs.

Research questions

Primary questions:

1) What is the main effect of using behaviourally enhanced messages, compared to the currently used DAQI messages, to present the health advice associated with air quality notifications for a hypothetical high air pollution scenario on adherence intentions?

Prediction:

A) The behaviourally enhanced messages will lead to stronger intentions to adhere to recommendations.

2) What is the main effect of using a behaviourally enhanced message, compared to the currently used DAQI messages, to present the health advice associated with air quality notifications on actual behaviour changes at four weeks?

Prediction:

A) The enhanced messages will lead to greater behaviour changes.

3) In case of a real alert being issued during the study period, how do the different messages affect actual behaviour change?

Prediction:

A) The enhanced messages will lead to greater behaviour change.

Secondary questions:

4) If there is a format effect, which variables mediate the relationship between the information format and behaviour change?

5) Which factors are associated with greater behaviour change across all groups?

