5.4 STUDY PROCEDURE

5.4.1 CityAir smartphone application

This is an application designed and developed by the City of London Corporation and King's College London. The CityAir app version 2.0.4 (available at: <https://www.cityoflondon.gov.uk/business/environmental-health/environmental-protection/air-quality/Pages/New-CityAir-App.aspx>) is currently available for iOS and Android and is compatible with iPhone, iPad and iPod touch and Android devices. This application allows users to sign up for air pollution alerts and find less polluted routes when levels of air pollution are high in London. In addition, it provides users with targeted advice for generally healthy and at risk individuals on how to reduce exposure to air pollution. Such advice is based on the official UK AQIs. The application also provides simple advice for users registered as cyclists, pedestrian, jogger, drivers, and businesses on how to reduce emissions and exposure (e.g. advice for drivers: 'Turn off your engine when parked'; for joggers: 'Consider delaying your jog till pollution levels are lower'; for businesses: 'Check out the CityAir guides to help lower pollution levels in the City').

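### A 'no' to the alert-period behaviour items mixes people who ignored the alert with people who had already switched or had nothing to change, which dilutes and may bias the question 3 comparison

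*Combined protocol and SAP*

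**What the plan says.** Section 4 lists as its third primary question: "In case of a real alert being issued during the study period, how do the different messages affect actual behaviour change". The measure is in Table 4 of section 5.6, in the air alert block. Under the stem "In response to receiving the air quality alert" there are five items: less outdoor activity, a different travel route, a different exercise location, a different travel time and a different exercise time. A typical item reads "I changed my travel route". The table note gives the response set: "Possible answers: yes, no, not sure". After the items comes "If you answered no, please report the reasons [text box".

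Section 6.1 compares the proportion reporting change between groups by chi-square, for a real moderate episode. It states no denominator, no treatment of 'not sure' and no recoding. It does not say whether the five items are tested singly or combined. Section 6.2 uses free text for content analysis of barriers and facilitators only.

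The plan expects that people may change habits for good. The planning item, at baseline and at four weeks, asks "have you considered making permanent changes to your daily travel route or exercise place and time". It records whether a change was considered, not whether it was made. Table 3 (section 5.5) gives examples of the additional messages sent to the intervention group alone, such as "Start by exploring green areas and parks close to your house or office".

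**The concern.** A 'no' can mean three different things: the person ignored the alert, was already protected by an earlier change, or had no journey or outdoor exercise to alter. Only the first is non-adherence.

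Two consequences follow, and they differ in kind.

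- **Dilution.** People with nothing to change, and people who had switched before enrolment, should be balanced by randomisation. They shrink the difference between the arms and cost power.
- **Possible bias.** Switching after randomisation but before an alert need not be balanced. The additional messages promote side streets and parks in general terms, not as a reaction to one alert, and only the intervention group gets them. If they produce lasting changes, those changes lower that arm's count of alert responses.

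The same block of Table 4 handles applicability elsewhere. The medication items are restricted to people with lung problems, and the recall item has an answer for people who received no alert. The travel and exercise items have no equivalent.

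**Working it through.** The sample size in section 5.3 is expressed as an effect size f with one covariate, so the plan has no figure for question 3 to reproduce. What follows is an illustration.

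**Inputs**
- 100 per arm: section 5.3 aims for 240 after 20% inflation, and 240 / 1.2 = 200, split equally (assumed). Fewer may answer an alert questionnaire.
- Control rate 36%: the median adherence rate for reducing or rescheduling outdoor activity in section 1.1.5. It is not a design assumption of the trial and does not refer to route or location change.
- Enhanced rate 56%: assumed, chosen to give roughly 80% power.
- Shares who cannot answer 'yes': assumed; the documents give none.

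**Formula** (two-sided 0.05, n per arm, p̄ the mean of p1 and p2)

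Power = Φ[(|p2 − p1| − 1.96·√(2p̄(1 − p̄)/n)) / √((p1(1 − p1) + p2(1 − p2))/n)]

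**Reference case.** 36% v 56%, p̄ = 0.46: (0.20 − 1.96 × 0.0705) / 0.0690 ≈ 0.896, so power is 81.5%.

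**Nothing to change, 30% in both arms**
- Counted as no change: 0.36 × 0.7 = 25.2% and 0.56 × 0.7 = 39.2%. The gap is 14 points and power 56.4%.
- Removed from the denominator: 36% v 56% with 70 per arm. The gap is back to 20 points and power is 66.4%.

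**Lasting switch after randomisation.** Multiply each arm's rate by one minus the share of its changers who had already switched and so answer 'no'.

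| Share switched, enhanced | Share switched, control | Observed rates | Gap (points) | Power |
|---|---|---|---|---|
| 10% | 10% | 32.4% v 50.4% | 18.0 | 73.7% |
| 10% | 0% | 36.0% v 50.4% | 14.4 | 53.8% |
| 20% | 20% | 28.8% v 44.8% | 16.0 | 65.2% |
| 20% | 10% | 32.4% v 44.8% | 12.4 | 43.6% |
| 20% | 5% | 34.2% v 44.8% | 10.6 | 33.4% |
| 20% | 0% | 36.0% v 44.8% | 8.8 | 24.4% |

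The result depends mainly on how far the shares differ between arms. Equal switching costs some power; unequal switching costs much more and shifts the estimate itself.

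**The case against.** The strongest reply is that the reasons are collected. The text box follows a 'no', and answers such as having already switched or having made no trip would be recorded there. That stands, and it means the information is not necessarily lost. But nothing in section 6 links it to the chi-square, so recoding from it later would be a post hoc choice.

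Second, a reader might infer that the plan scores these people as showing no change. It does not say so. That treatment follows for anyone who answers 'no', because the analysed quantity is the proportion reporting change. For 'not sure' it is simply undefined. If the five items were combined as any change, a person who had switched route could still score through another item.

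Third, a reader might infer that question 3 is biased against the enhanced messages. The documents do not establish this. For someone who switched in week 1, 'no' is a true answer to a question about the alert. Section 5.4.1 says the app helps its users find less polluted routes, and controls are users of that app, so no switching among controls is an extreme case. The timing of the additional messages is not stated either. Question 2 separately measures action over four weeks, so the messages are not judged on question 3 alone, although that does not repair question 3.

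Finally, 36% is an overall rate from the review and may already include people with nothing to change, in which case a further 30% reduction overstates the dilution.

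**Conclusion.** The point holds as a measurement weakness in a primary question. The three answers cannot separate non-adherence from earlier change or from having nothing to change, and the plan has no rule that uses the text box to do so.

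Dilution follows wherever not-applicable people, or people who switched before the study, answer 'no' and stay in the denominator. Bias against the enhanced arm is plausible but conditional: it needs more lasting switching after randomisation in that arm than among controls. Under the illustrative rates, 30% with nothing to change takes power from 81.5% to 56.4%. Switching by 20% of enhanced-arm changers leaves between 65.2% and 24.4%, depending on the control share. These figures show scale only. The true shares, and so the size and direction of any bias, cannot be obtained from the documents.

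**What to change.** - **Answers.** Add to the alert-period travel and exercise items: 'already changed since joining this study', 'already did this before the study' and 'no such trip or exercise'. Report each by arm.
- **Denominator.** Add a baseline question on usual travel and outdoor exercise, and use it to define who each item applies to. Answers given after the alert should not set the denominator, because the messages may affect them. The app already distinguishes "simple advice for users registered as cyclists, pedestrian, jogger, drivers, and businesses", but section 5.4.1 says the study will not separate cyclists, joggers and pedestrians, so a direct question is cleaner. Baseline data cannot show whether a trip was due on the alert day, so some dilution will remain.
- **Outcome.** Keep 'yes' in response to the alert as the main question 3 outcome. Pre-specify a second analysis that counts 'yes' plus 'already changed since joining' as protective change. That is a different estimand (change since enrolment, not response to an alert) and should be labelled so.
- **Scoring.** State how 'not sure' and skipped items are handled, and whether items are tested singly or combined.
- **Fallback.** If the questionnaire cannot be altered, pre-specify coding of the text box, done blind to arm, and how the codes enter the analysis.

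The cost is slightly longer questionnaires, one extra analysis and a smaller denominator for some items.
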